## 2.0 Background

We plan to prospectively study breast tissue changes after a short course of Tamoxifen (Tam). Women with atypical hyperplasia (AH) and lobular carcinoma in situ (LCIS) are at increased risk of breast cancer (BC) (~1-2 % per year). Over two decades ago, placebo-controlled randomized trials established that oral tamoxifen (20 mg/day) reduces breast cancer risk by 50% in generally defined high risk women, with ~70% reduction in women at high risk specifically due to atypical hyperplasia.[1] Years later, the side effects and toxicity of oral tamoxifen at 20 mg/day remain a significant barrier to its uptake and long-term compliance.[2, 3] To address the issue of toxicity, two main strategies have been pursued: 1) using a lower dose of oral tamoxifen, and 2) using a topical formulation of tamoxifen to avoid systemic side effects. Here we will perform a prospective study of women with AH, LCIS, or increased risk of BC based on risk model calculations concordant with current consensus guidelines (described in detail below) who will take a short course of prevention therapy; breast tissue samples will be evaluated pre- and post-therapy to identify and evaluate very early biomarkers of response. The overall goal of the study is to evaluate short- term changes in background breast tissue induced by either low-dose oral tamoxifen or topical 4-OHT gel in women with AH, LCIS, or increased risk of BC based on risk model calculations.

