## Reduction in mammographic density after tamoxifen use is associated with decreased BC risk.

Tam has consistently been shown to reduce mammographic density.[25-28] Our group recently demonstrated reductions in volumetric density in breast cancer patients after one year of treatment with Tam or aromatase inhibitors.[29] Importantly, these reductions in mammographic density after prevention therapy have been shown to be associated with decreased risk of later breast cancer in high risk women taking Tam for prevention,[30] as well as reduced recurrence and mortality in breast cancer patients taking Tam as adjuvant therapy.[25-28] Thus, in the planned study we will assess change in area and volumetric density measures from mammograms to determine if changes are detectable after only one month of treatment. Early imaging changes are a feasible potential endpoint, since short-term Tam use can induce detectable breast changes with sound speed ultrasound tomography after 1-3 months,[31] on MRI within 90 days,[32] and on molecular breast imaging (MBI) at 4 weeks (**Fig 1**).

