## Background Parenchymal Uptake (BPU) on MBI is a promising noninvasive imaging biomarker of response.

Molecular breast imaging (MBI) is a low-radiation dose nuclear medicine test that uses a high-resolution, semiconductor-based gamma camera to image the uptake of Tc-99m sestamibi in the breast.[33] As MBI is a functional imaging technique that relies on differences in preferential uptake of Tc-99m sestamibi in metabolically-active cells, it is able to reveal cancers hidden among dense fibroglandular tissue on a mammogram (published incremental cancer detection of 7.5-16.5 per1000 women screened).[34, 35] In addition to detecting BC, MBI also depicts the level of Tc-99m sestamibi uptake in non-cancerous background fibroglandular tissue, termed background parenchymal uptake (BPU). BPU is subjectively assessed according to a validated lexicon as one of four categories (photopenic, minimal to mild, moderate, and marked), with high reader agreement (inter-reader  $\kappa=0.84$ , intra-reader  $\kappa=0.87$ ) that describe the relative intensity of uptake in fibroglandular tissue.[36, 37] Importantly, BPU was recently shown to be associated with BC risk; women with moderate or marked BPU have 3.4 to 4.8-fold increased risk compared to women with photopenic or minimal-mild BPU, even when adjusted for percent mammographic density and hormonal influences. The exact mechanism of uptake of Tc-99m sestamibi in breast tissue is not entirely understood, but has been correlated with blood flow, mitochondrial activity, and mitotic activity in BCs.[38, 39] In a recent study led by [name], women with high BPU on screening MBI underwent 4 weeks of low-dose (5 mg or 10 mg) oral tamoxifen, with early decreases in BPU (**Fig 1**).[40] Therefore BPU is promising as a non-invasive measure of proliferative activity in the breast tissue.

[figure not shown]

Figure 1. Images from a patient with mammographically dense breasts undergoing supplemental screening with MBI (A,B) and MBI again after 4 weeks low-dose (5 mg) oral tamoxifen (C).

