#### 5.0 Test Schedule

Test & Procedures	Baseline	End of Treatment (at the end of 4 weeks of treatment) 
Pregnancy Test (serum or urine)	X 	
Follicle stimulating hormone (FSH)	X 	
Baseline labs [CBC and Liver Function testing (ALP, ALT, AST, ALB, TP, BILI), creatinine coagulation labs (fibrinogen, Antithrombin 3)]	X 	X 
Physical Examination	X 	X 
Two 10 ml amounts of blood (will be stored for future research)	X 	X 
Blood Draw (4-OHT bioavailability)		X 
Research Biopsy of Breast Tissue - same quadrant as diagnostic biopsy  [Ki67, NanoString, 4-OHT bioavailability (post-treatment only);] Pretreatment diagnostic biopsy is OPTIONAL if meets requirements	X 	X 
Digital Screening Mammogram	X 	X 
MBI (Mayo Clinic site only)	X 	X 
BCPT Symptom Survey	X 	X 
Symptom /safety/AE assessment	X 	X 

1. For women of childbearing potential only.
2. Research Funded (Note: clinical surgical consult will not be research funded.)
3. For women with unknown menopausal status
4. Physical exam could be done within 3 months before treatment starts.

5. Blood for storage two 10 ml blood draws using purple top EDTA tubes – protect from light exposure (i.e., wrap in tin foil, use light sensitive brown bags). **First EDTA tube**- Aliquot (1) 4000uL blood pour for DNA extraction. Refrigerate, Centrifuge at lab standards. Process for three 1 ml aliquots of plasma into 3 cryovials 1 ml plasma each and 1ml WBC. Light Sensitive. Store in -80 freezer. **Second EDTA vial** is stored as whole blood.
6. Blood for 4-OHT bioavailability. 4 ml. green top heparin tube. Process for plasma. Protect from light exposure as light sensitive (i.e., wrap in tin foil, use light sensitive brown bags). Store in -80 freezer.
7. Baseline Pretreatment research tissue core biopsy information is located in Appendix F.

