*Feasibility.* At Mayo Clinic in Rochester, MN, we see an average of 55 patients per year with ADH or ALH who would be eligible for this study. At Mayo Clinic, Drs. [name], [name], and [name] have successfully led accrual of over 500 women to prospective studies in the last six years, therefore successful accrual of women to this prospective study is feasible. At Northwestern University, there is a similar volume of women with diagnoses of ADH or ALH, and they have accrued ~400 women over five years to various studies requiring some form of intervention (either medication or biopsy). Accrual plan is for 42 subjects at Mayo Clinic, 42 at Northwestern University and 20 subjects at MD Anderson Cancer Center at Cooper. With an anticipated timeframe of 48 months to complete accrual, this averages to 1-2 patients per month per site. This study should be acceptable to patients as the duration of intervention is short and therefore short-term

toxicity is expected to be limited to only temporary vasomotor symptoms.

*Translational studies.* The primary endpoint will be change in Ki67 in background normal breast lobules (% cells positive by Aperio quantitation). Additional endpoints will include changes in volumetric density (% and dense volume) measured using VolparaTM both at baseline and after four weeks of treatment. In addition, promising genes from discovery work in Aim 2 will be evaluated using NanoString.

Changes in background parenchymal uptake (BPU) on MBI will also be employed as an exploratory endpoint. Blood samples and residual breast tissues collected pre/post Tam will be stored for future correlative studies.

*Endpoints.* The primary endpoint is change in Ki67 level pre/post treatment. The primary analysis for the primary endpoint will include all eligible patients who began study drug intervention and have available tissue measures of Ki67 levels at both timepoints (pre- and post-treatment).

A sensitivity analysis for the primary endpoint will also be performed. This sensitivity analysis will include eligible patients who have available tissue measures of Ki67 levels at both timepoints and were compliant with study treatment. Patients will be classified as non-compliant with the study treatment (and thus excluded from the sensitivity analysis) using criteria outlined above (patients who have less than 80% compliance with daily drug use or have missed more than 3 doses in the final 14 days).

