*Statistical analysis.* The primary hypothesis is that the reduction seen with 4-OHT gel will be *not inferior* to that seen with oral tamoxifen. We also hypothesize that oral tamoxifen and 4-OHT gel will each be superior to placebo with respect to the percent change in Ki67 in background normal lobules between baseline and four weeks. Analyses will assess if significant changes in Ki67 are observed after four weeks of treatment by paired t-tests/Wilcoxon signed rank tests, stratified by treatment group. We will assess the non-inferiority of 4-OHT gel compared to oral tamoxifen by estimating a 95% confidence interval for the mean *difference* in percent change between the two agents after four weeks of treatment; if the lower limit of the confidence interval is less than the non-inferiority margin (described below), we will conclude that 4-OHT gel is non-inferior to oral tamoxifen. As exploratory analyses, we will assess pairwise differences between samples on active treatment (oral tamoxifen or 4-OHT gel, separately and combined) vs. placebo using two-sample t-tests/Wilcoxon rank sum tests. Similarly, we will assess changes from baseline in the expression of the candidate genes identified in Aim 2 (absolute log2 fold-change > 2 and/or q-value < 0.05). Volumetric density changes from baseline within treatment group will be assessed continuously, and evaluated using paired t-tests on the log-transformed density or Wilcoxon signed-rank tests; pairwise differences between treatment groups will be assessed with two-sample t-tests/Wilcoxon rank sum tests. BPU on MBI is measured as a four category ordinal scale; we will compare pre-to-post changes within group using Wilcoxon signed rank tests and will compare the percent of subjects decreasing BPU category by one or more level between groups using chi-square tests. We will assess the correlation between changes in volumetric density and changes in BPU, using Spearman correlation. Symptoms from the BCPT survey are measured on a five-level ordinal scale. We will compare differences in pre- to post-treatment symptom severity changes across

treatment arms using Wilcoxon rank sum tests.

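### The one planned correlation between markers, density change with BPU change, does not account for treatment arm, so a drug effect on both would appear as association

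*Combined protocol and SAP*

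**What the plan says.** Under Statistical analysis in Section 11.0, after the within-group and between-group tests for each marker, the plan adds: "We will assess the correlation between changes in volumetric density and changes in BPU, using Spearman correlation". It does not say whether this is done within arm, adjusted for arm or pooled. The neighbouring within-group tests of Ki67, density and BPU are each tied explicitly to treatment group. This is the only planned analysis relating one marker to another. Nothing relates BPU change or density change to Ki67 change.

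The same section says "BPU on MBI is measured as a four category ordinal scale" and "Changes in background parenchymal uptake (BPU) on MBI will also be employed as an exploratory endpoint", although Section 3.0 lists BPU under the secondary aims. MBI is done at Mayo only (Section 5.0), where 42 women are planned. Allocation is 2:2:1 to oral tamoxifen, gel and placebo.

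The Background gives several grounds for measuring BPU. One is risk: "Importantly, BPU was recently shown to be associated with BC risk". Another is an early fall on four weeks of low-dose tamoxifen. It closes with "Therefore BPU is promising as a non-invasive measure of proliferative activity in the breast tissue". For density the reason is different: "to determine if changes are detectable after only one month of treatment".

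**The concern.** A correlation between two change scores across arms has two sources. One is association between women on the same treatment, which is the question of interest. The other is the difference between arm means. If active drug lowers both density and BPU, treated women sit low on both and placebo women sit high on both, so the pooled correlation is positive without any association within arm.

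A reader of the trial report would probably take a positive coefficient to mean that density and BPU respond together in the same women. Part or all of it could be the treatment effect on each measure, which the plan already tests separately. No primary or safety conclusion is affected. What is at stake is how one exploratory result is read.

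**Working it through.** The plan states no sample size, power or precision for any correlation, so there is no figure of its own to reproduce.

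**Inputs from the documents**
- Share on active drug under 2:2:1: p = 4/5 = 0.8, so q = 0.2 and pq = 0.16.
- Women with MBI: 42 planned at Mayo. After the plan's 15% allowance, 42 × 0.85 = 35.7, about 36.

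**Inputs assumed**
- Density shift on active drug relative to placebo: d = 0.3, 0.5 or 1.0 within-arm SD.
- Share of women on active drug falling one BPU category: 30%, 50% or 70%; on placebo, 5%.
- Both active arms shift equally, and the two changes are independent within arm.

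**Step 1. Correlation produced by pooling.** With BPU change coded as fall or no fall, let D be the active-minus-placebo difference in the share falling and P the overall share falling. Then

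r = pq·d·D / √[(1 + pq·d²)·P(1 − P)]

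- Smallest case (30%, d = 0.3): D = 0.25 and P = 0.8 × 0.30 + 0.2 × 0.05 = 0.25. r = 0.16 × 0.3 × 0.25 / √(1.0144 × 0.1875) = 0.0120/0.436 = 0.03.
- Largest case (70%, d = 1.0): D = 0.65 and P = 0.8 × 0.70 + 0.2 × 0.05 = 0.57. r = 0.16 × 1.0 × 0.65 / √(1.16 × 0.2451) = 0.104/0.533 = 0.195.

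Simulation of the pooled Spearman coefficient agrees:

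| Active women falling a category | d = 0.3 | d = 0.5 | d = 1.0 |
|---|---|---|---|
| 30% | 0.03 | 0.04 | 0.09 |
| 50% | 0.04 | 0.07 | 0.14 |
| 70% | 0.06 | 0.10 | 0.19 |

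Treating both measures as continuous gives r = pq·d₁d₂ / √[(1 + pq·d₁²)(1 + pq·d₂²)]. With equal shifts this is 0.01 at 0.3 SD, 0.04 at 0.5 SD, 0.09 at 0.8 SD and 0.14 at 1.0 SD.

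**Step 2. Effect on a test at n = 36.** With no association within arm, the unadjusted Spearman test at a nominal 5% rejects in about 5% to 10% of simulated trials when d is 0.5 or less. In the largest case, repeat runs give 19% to 22%. A partial Spearman correlation (both variables ranked, arm removed from each) rejects in about 5% to 6% throughout.

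**Step 3. Precision available for any correlation with BPU.** Using Fisher's z with Spearman variance 1.06/(n − 3), the smallest |rho| detectable with 80% power at two-sided 5% is tanh[(1.96 + 0.84)·√(1.06/(n − 3))].

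- n = 36: tanh(2.80 × 0.179) = 0.46.
- n = 42: tanh(2.80 × 0.165) = 0.43.
- Adjusting for three arms replaces n − 3 by n − 5, which gives 0.48 and 0.44.
- An observed 0.30 at n = 36 has a 95% interval of tanh(0.310 ± 1.96 × 0.179), or about −0.04 to 0.58.

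Ties on the four-level scale would widen all of these.

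**The case against.** The plan is silent on arm and does not say that the correlation is pooled. A pooled coefficient is also a legitimate descriptive quantity for an exploratory endpoint. The larger artefacts need shifts that may not occur in four weeks, and the documents give none for BPU or density. All of this is fair and limits the weight of the point. It does not remove it: the sentence can be run unadjusted, and its neighbours state the grouping while it does not.

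A reader might go further and infer that the trial cannot say whether BPU or density tracks proliferation. The documents do not support that, for four reasons.
- Paired Ki67 and imaging data will exist, for density at all sites and for BPU at Mayo. What is absent is a prespecified line, not the means.
- The Background sentence on early biomarkers, "breast tissue samples will be evaluated pre- and post-therapy to identify and evaluate very early biomarkers of response", concerns tissue markers and does not commit the trial to validating imaging against Ki67.
- Density is measured to see whether change is detectable at one month, and the plan tests that. It is nowhere presented as a proliferation marker.
- Proliferation is one of several grounds for BPU, and the formal aim is only its change from before to after treatment.

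Nor would a Ki67–BPU correlation settle the matter, given the precision in Step 3. Timing adds a further limit. Baseline Ki67 may come from a diagnostic biopsy up to 6 months before enrolment (Section 5.0, footnote 8). Baseline MBI is done within 7 days of starting treatment (Section 6.7), or an existing scan within one month is accepted (Section 5.0, footnote 11).

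**Conclusion.** The point holds in a limited form. The planned density–BPU correlation does not account for arm, and a drug effect on both measures would create a correlation of about 0.03 to 0.19 where none exists within arm. It is 0.10 or less for density shifts up to 0.5 SD. It approaches 0.2 only when density shifts by a full SD and 70% of treated women drop a BPU category. These figures rest on assumed shifts, equal effects in the two active arms and independence within arm.

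The absence of any Ki67–BPU analysis is a modest gap against the Background's closing remark on BPU, and adding one is optional. This is a minor improvement to an exploratory analysis.

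**What to change.** Replace the sentence in Section 11.0 with a partial Spearman correlation between change in volumetric density and change in BPU, adjusted for the three randomized arms, reported with a 95% confidence interval and labelled exploratory.

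Optionally, add the same arm-adjusted exploratory correlation for Ki67 change with BPU change in Mayo women. State beside it that it rests on about 36 to 42 women, that the detectable |rho| is about 0.43 to 0.46 at 80% power before ties and the small loss from adjustment, and that baseline Ki67 tissue may predate baseline MBI by months.

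The cost is a few lines of SAP text and code, with no new data, reads, procedures or sample size. The drawback of the optional line is one more imprecise exploratory estimate.

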#### **Updates to Sample size/power with 4OHT dose modification 10/12/22.**

We expect that the higher dose of 4OHT gel (8 mg/day) will be at least as effective as the original dose (4 mg/day), and therefore the primary endpoint, sample size, and power calculations remain the same and may even be conservative, assuming analysis including all subjects treated with 4OHT gel at either dose. We also plan to conduct sensitivity analyses for the primary endpoint excluding the 4mg/day group (this will be N=5 patients on the 4 mg/dose that would be excluded).

To date, 12 patients have been accrued (5 oral Tam, 5 4OHT gel 4 mg/day dose, and 2 controls). Subtracting these N=12 patients accrued from the total original planned sample size of N=104, there will be N=92 patients remaining to accrue who will be randomized after the 8 mg/day 4OHT gel dose is implemented, per existing 2:2:1 schema.

With anticipated sample size of 92 patients to be randomized after approval of the higher (8 mg/day) 4OHT gel dose, we estimate final total randomized numbers will be as follows: Total N=104, with 41 on oral Tam, 5 at the 4 mg/day dose of 4OHT gel, 36 at the 8 mg/day dose of 4OHT gel, and 22 dual-placebo controls.

#### **Anticipated power for the primary endpoint.**

Primary endpoint is noninferiority of Ki67 change between 4OHT gel and oral Tam arms.

For a combined analysis including ALL subjects receiving 4OHT gel at EITHER dose, ie 41 oral Tam versus 41 with 4OHT gel (5 at 4mg/day dose plus 36 at 8 mg/day dose), keeping the original assumption of 15% attrition results in final sample of 36 per group and power of 80%.

For a *subgroup analysis* including ONLY the subjects receiving the higher 8 mg/day dose of 4OHT gel, the power ranges from 76% to 82%, depending on the amount of attrition (see Table below).

**Table 1. Sample size and power considerations for primary endpoint, non-inferiority in Ki67 change between gel and oral**

	Sample size & power assuming 15% attrition	Sample size & power assuming 10% attrition	Sample size & power assuming 5% attrition	Sample size & power assuming no attrition
Use entire sample,	36 per group (Power: 80%)	37 per group (Power 81%)	39 per group (Power 83%)	41 per group (Power: 85%)

including subjects with either 4 mg/day or 8 mg/day 4OHT gel				
Subgroup analysis including only those with 8 mg/day dose	36 oral Tam group, 31 in 8 mg/day 4OHT gel group (Power 76%)	37 oral Tam group, 32 in 8 mg/day 4OHT gel group (Power 78%)	39 oral Tam group, 34 in 8 mg/day 4OHT gel group (Power 80%)	41 oral Tam group, 36 in 8 mg/day 4OHT gel group (Power 82%)

## 12.0 Descriptive Factors

Examination of differences between groups on BCPT will occur across study arms on the 8 identified scales and on additional items measuring fatigue and sexual function.

## 13.0 Treatment/Follow-up Decision at Evaluation of Patient

Reason Off Treatment
Study Complete
Adverse Event
Death
Disease Progression
Lost to Follow-up
Non-Compliance
Participant Withdrawal
Participant Refused Follow-up
Physician Decision
Protocol Defined Follow-up Completed
Protocol Violation
Ineligible
Other

### 13.1 Ineligible

A patient is deemed *ineligible* if the patient did not satisfy each and every eligibility criteria for study entry. If the patient received treatment, the patient may continue treatment at the discretion of the physician as long as there are not safety concerns. The patient will continue in the Active Monitoring/Treatment phase of the study.

### 13.2 Major Violation

A patient is deemed a *major violation*, if protocol requirements regarding treatment are severely violated that evaluability for primary end point is questionable. If the patient received treatment, the patient may continue treatment at the discretion of the physician as long as there are not safety concerns. The patient will continue in the Active Monitoring/Treatment phase of the study.

### 13.3 Withdrawal / Screen Failure

A patient is deemed a *withdrawal* if she meets all eligibility criteria, consented to

participate, and is removed from the study or chooses not to participate for any reason. A patient is deemed a screen failure if she fails to meet all study inclusion / exclusion criteria, whether consented or not. Reasons for withdrawals and screen failures will be recorded in the study database.

Patients who withdraw from the study will be offered follow-up for resolution of adverse events, and this will consist of telephone or in-person visit evaluation as clinically needed and agreed upon by the patient.

If a patient withdraws from the study prior to initiating any of the study drug interventions, then she may be replaced with another patient toward the accrual total. If a patient withdraws from the study AFTER initiating any of the study drug interventions, then she will not be replaced with another patient toward the accrual total.

